## **Section 6: Study Procedures**

### **6.1 Informed Consent/Assent and HIPAA Authorization**

Informed consent is a process that is initiated prior to the individual's agreeing to participate in the study. It continues throughout the individual's study participation. Consent forms describing in detail the study intervention, study procedures, and risks will be given to the participant. Written documentation of informed consent will be required prior to starting intervention/administering study intervention. Child assent form and informed consent form will be submitted with this protocol. Consent forms will be Institutional Review Board (IRB)-approved and the participant/legally authorized representative (LAR) will be asked to read and review the document. The principal investigator and co-investigator will explain the research study to the participant and answer any questions that may arise. This conversation will take place in a private room. Assent will be conducted for patients 12 years of age. A verbal explanation will be provided in terms suited to the participant's comprehension of the purposes, procedures, and potential risks of the study and of their rights as research participants. Participants/families/LAR will have the opportunity to carefully review the written consent form and ask questions prior to signing. The participants/family/LAR should have the opportunity to discuss the study with their family or surrogates, or think about it prior to agreeing to participate. The participant's caregiver or LAR will sign the informed consent document and the participant will sign the Assent form prior to any procedures being done specifically for the study. Assent for subjects aged 8-12 years old will be obtained and documented on the parental/LAR consent form.

Participants/families/LAR must be informed that participation is voluntary and that they may withdraw from the study at any time, without prejudice. A copy of the informed consent and assent documents will be given to the participants/families/LAR for their records. The rights and welfare of the participants will be protected by emphasizing that the quality of their medical care will not be adversely affected if they decline to participate in this study.

## **6.2 Screening Process**

Patients scheduled for routine clinical diabetes appointments will all be screened for participation up to 90 days prior to the scheduled visit using chart review. This will be conducted in accordance with the HIPAA rules. Those meeting inclusion criteria based on chart review will be discussed with their provider to assess confidence that the potential participant can successfully operate the CGM and is capable of adhering to the protocol. Suitable participants identified through screening will be approached in person to participate at the time of a clinic appointment. Patients and families who are still considering whether to enroll after the clinic appointment will be contacted by phone after the visit.

Before completing any procedures or collecting any data that are not part of usual care, written informed consent will be obtained. Informed consent will be obtained in a manner that will minimize undue influence or coercion and will allow participants sufficient time to review the document and answer questions before signing. Ideally all discussion of the study will be conducted in person, however in the event that this is not possible the research team will contact participants via phone within 28 days of initially discussing the study.

A caregiver/legal guardian (referred to subsequently as “caregiver”) will be provided with the Informed Consent Form to read and will be given the opportunity to ask questions. Potential participants will be given a Child Assent Form to read and discuss with his/her caregiver and study personnel. If the parent and child agree to participate, the Informed Consent Form and Child Assent Form will be signed, either in person or electronically via REDCap. A copy of the consent form will be provided to the participant and his/her parent and another copy will be added to the participant’s study record.

As part of the informed consent process, each participant will be asked to sign an authorization for release of personal information. The investigator, or his or her designee, will review the study-specific information that will be collected and to whom that information will be disclosed. After speaking with the participant, questions will be answered about the details regarding authorization. A participant is considered enrolled when the informed consent form has been signed.

## **6.3 Study Interventions and Follow-Up**

### Enrollment visit

Those who have met eligibility criteria and express interest in study participation will meet with study staff to review the study specifics in more detail and obtain consent. Randomization will occur after consent has been obtained. A blinded Dexcom G6 pro

CGM will be placed on the patient and be worn for 10 days in order to collect baseline data prior to starting the SMA intervention. Phone applications that will allow for sharing of CGM data between patients and the diabetes clinical care team will be downloaded and established before the end of the visit.

#### Initial SMA visit

After enrollment is complete, data will be collected from routine clinical care, including height, weight, BMI, and a point of care fingerstick A1c. A battery of validated survey measures exploring diabetes-specific quality of life will be completed by the parent and youth, including: T1DAL, DSMP, SEDS, PAID, CGM benefits and burdens, and an SMA evaluation. The caregiver will be asked to complete parental versions of the P-T1DAL, P-DSMP, P-PAID, P-SEDS, CGM benefits and burdens, and SMA evaluation. Surveys will be completed by caregiver, preferably the one most involved in medical care, but not both. If the caregiver elects not to complete these measures the patient is still eligible to participate in the study. Participants will have the option to complete these measures online or in clinic. Secure REDCap surveys will be sent to participants via email 1 week before their visit. If the survey has not been completed at the time of the visit, the participant will be given the option to complete the measures using an iPad or paper in clinic at the time of their visit.

The structure of the group visits will be reviewed with patients and families, and all members of the diabetes team will introduce themselves and explain their role in diabetes care. As some patients will be CGM naïve at this visit, education will focus on insertion and removal of the CGM along with appropriate use of the CGM receiver, alerts and alarms, data sharing, and troubleshooting common CGM problems. Established sharing of CGM data between patients and the diabetes clinical care team will be confirmed before the end of the visit. The group visit will conclude with a review of the core concepts discussed, and patients will set goals for the next SMA. After completing the visit, patients will continue using the CGM for diabetes management.

#### Follow up SMA at 3, 6, 9, and 12-months

Follow up SMA will be scheduled 3, 6, 9 and, 12 months from the initial group visit. Data will be collected from routine clinical care, including height, weight, BMI, and a point of care fingerstick A1c. Survey measures will be completed again as described previously. CGM data will be analyzed for the 14 days preceding each visit. Chart review from the time of the initial baseline visit will be conducted to assess the incidence of DKA, severe hypoglycemia, ED visits, and hospital admissions. Details obtained from the chart review will be confirmed with participants. Data from the CGM will be obtained through online software used to securely query these devices for routine clinical care (Dexcom Clarity).

Discussions and education guided by the facilitators will focus on issues that have been described in the literature as potential barriers to CGM use and adherence. Recurrent alerts and alarms can result in alarm fatigue, and falsely low glucose readings and sensor or transmitter failures have been cited as reasons for discontinuing CGM use. The continuous nature of CGM data has been shown to place significant demands on patients and their families, and to create stress related to the constant need for

diabetes-related attention. Follow up visits will focus on optimized use of CGM alarms and prevention of alarm fatigue. Psychologists and CDCES will discuss strategies to cope with the on-body presence and potential embarrassment resulting from CGM wear and to optimize parent-child communication surrounding CGM. Nutritionists will highlight the impact of different foods on glycemic trends and discuss strategies to optimize control. SMA will also allow ample opportunity to jointly review deidentified CGM reports and how to effectively interpret data and make management changes in response to CGM data, empowering patients and families to improve self-management and reduce stress related to CGM use. Active participation in discussions and group exercises will continue to strengthen the community feeling and social support network within the SMA group. Any participant that chooses to discontinue CGM during the 12 month study period will wear a blinded CGM 10 days prior to the follow up visits to allow for complete data collection.

If a visit is missed by the participant, he/she will have the option to attend a different group's SMA that corresponds to the same timing as the SMA that was missed. In the event of withdrawal or early termination, participants will be asked to come for an end of study visit. If any participant chooses to discontinue CGM use, they will be asked to wear a blinded CGM for each of the 10 day periods ahead of their planned clinic visits.

Upon completion of the final SMA visit at month 12, dyads will be contacted to schedule a semi-structured interview and will then return to standard clinical care. A structured focus group guide consisting of broad, open-ended questions to elicit details from patients and parents will be provided to facilitators. These sessions will last 45 minutes ( $\pm$  15 minutes). The sessions will be recorded on two separate devices and subsequently transcribed to allow for data analysis.

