### **Privacy Concerns**

Data downloaded from the CGM will be collected for the study as measures of diabetes self-management behaviors. Some people may be uncomfortable with the researchers' having such detailed information about their daily diabetes habits, however this too is part of routine diabetes care. The group setting of the SMA removes much of the privacy that is provided to patients and their families during a routine individual visit. Some families might feel uncomfortable talking about personal experiences or attitudes related to their own diabetes care in front of other people. Description of the SMA will be clear during the consent process so that only families who are comfortable sharing in a group setting will choose to participate in the study. Participants and their caretakers will also have the option to withdraw from the intervention at any time if they become uncomfortable with the lack of privacy in the SMA.

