### 3.3 Primary Outcome Measure(s)

Given the novelty of the SMA approach for underserved youth and promotion of CGM technology uptake and sustained use, feasibility and acceptability of the intervention will serve as the primary outcome measure. We will track recruitment, enrollment, participation, and retention through a CONSORT table (Table 2) for the intervention group. Feasibility benchmarks include: recruitment (>60% of reached/eligible

participants), CGM initiation, (>80%), SMA sessions attended (>80%), and retention (>80%). In addition, feasibility encompasses demographic characteristics of the enrolled sample, with enrollment and overall increased uptake of CGM among youth from historically underrepresented racial and ethnic backgrounds (Black race and/or Latinx ethnicity) and income levels. Attrition data and team feedback will help determine how recruitment rates may be improved. Acceptability will be assessed using satisfaction surveys and determined by a high level of satisfaction with participation, perceived utility of the intervention content, and perceived benefit from participation (>80% reporting that they were satisfied and perceived utility and benefit). We will report summary statistics on each feasibility and

acceptability item in the questionnaires (mean and standard deviation as well as percent answering a specific Likert level). Acceptability also will be examined by key demographic characteristics, including participant age and race/ethnicity.

Parent-child dyads will participate in semi-structured interviews to assess satisfaction with the SMA. Thematic analysis of qualitative data will be conducted by two team members who will independently review interview transcripts to generate initial codes. Initial codes will be discussed by the group to generate a list of second-cycle codes and each team member will then apply the coding framework to all transcripts before

**Table 2.** Analytical plan for Aim 1, feasibility and acceptability.

Construct	Measure	Interval
Recruitment	# referred	Study initiation through completion of recruitment
Feasibility/	# screened	
Acceptability	# enrolled % eligible who enroll	
Intervention	#/% sessions attended	SMA visits every 3mo
Feasibility		
Intervention	Child/parent satisfaction ratings	After completion of intervention
Acceptability	Child/parent qualitative interview	
Retention	% who initiate CGM	All assessment time points

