### **5.7 End of Participation Criteria and Procedures**

Participants are free to withdraw from participation in the study at any time upon request. The reason for participant discontinuation or withdrawal from the study will be recorded on the Premature Termination Case Report Form (CRF). Subjects who sign the informed consent but do not receive the study intervention may be replaced. Subjects who sign the informed consent form, begin the study intervention, and subsequently withdraw, or are withdrawn or discontinued from the study, will try and be replaced.

Participants who experience significant psychological distress as a result of the intervention or whose presence at SMA visits will be terminated from study participation. Anyone experiencing psychological distress will be referred to the diabetes psychology team for support (Drs. [name] and [name], Co-I's).

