### **Primary Outcome**

Given the novelty of the SMA approach for underserved youth and promotion of CGM technology uptake and sustained use, feasibility and acceptability of the intervention will serve as the primary outcome measure. We will track recruitment, enrollment, participation, and retention through a CONSORT table (Table 2) for the intervention group. Feasibility benchmarks include: recruitment (>60% of reached/eligible participants), CGM initiation, (>80%), SMA sessions attended (>80%), and retention (>80%). In addition, feasibility encompasses demographic characteristics of the enrolled sample, with enrollment and overall increased uptake of CGM among youth from historically underrepresented racial and ethnic backgrounds (Black race and/or Latinx ethnicity) and income levels. Attrition data and team feedback will help determine how recruitment rates may be improved. Acceptability will be assessed using satisfaction surveys and determined by a high level of satisfaction with participation, perceived utility of the intervention content, and perceived benefit from participation (>80% reporting that they were satisfied and perceived utility and benefit as indicated by a Likert scale score of 4 or 5). We will report summary statistics on each feasibility and acceptability item in the questionnaires (mean and standard deviation well as percent answering a specific Likert level). Acceptability also will be examined by key demographic characteristics, including participant age and race/ethnicity.

Parent-child dyads will participate in semi-structured interviews to assess satisfaction with the SMA. Thematic analysis of qualitative data will be conducted by two team members who will independently review interview transcripts to generate initial codes. Initial codes will be discussed by the group to generate a list of second-cycle codes and each team member will then apply the coding framework to all transcripts before identifying dominant themes. ATLAS.ti software will be used to organize and analyze the qualitative data.

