### **8.2 Statistical Hypotheses**

Primary Outcome: feasibility and acceptability of SMA among underserved youth with T1D.

Hypothesis 1a. Rates of SMA retention (>80%) at 12-months and satisfaction with visits (>80%) will be high.

Null Hypothesis 1a: n/a

Hypothesis 1b: Thematic analysis of semi-structured interviews will identify high satisfaction with SMA.

Null Hypothesis 1b: n/a

Secondary Outcome: preliminary impact of SMA on glycemic control, self-management skills, self-efficacy, diabetes related quality of life, and treatment satisfaction among underserved children with T1D and their caregivers

Hypothesis 2a: CGM percentage wear time and sustained use, as defined by use within the 2 weeks prior to the visit, will be greater upon completion of the SMA intervention at 12 months compared to baseline

Null Hypothesis 2a: CGM percentage wear time and sustained use, as defined by use within the 2 weeks prior to the visit, will not be significantly different upon completion of the SMA intervention at 12 months

Hypothesis 2b: CGM time in range (70-180 mg/dL) will be greater and the glucose management indicator (GMI) lower for youth upon completion of the SMA intervention group at 12 months compared to baseline.

Null Hypothesis 2b: CGM time in range (70-180 mg/dL) will not be significantly different upon completion of the SMA intervention at 12 months

Hypothesis 2c: Diabetes-specific quality of life, self-management behaviors, and self-efficacy scores will be greater upon completion of the SMA intervention at 12 months compared to baseline.

Null Hypothesis 2c: Diabetes-specific quality of life, self-management behaviors, and self-efficacy scores will not be significantly different upon completion of the SMA intervention at 12 month

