## **8.5 Sample Size**

As this is a pilot study, we plan to enroll up to 20 parent-child dyads. We anticipate low dropout rates, but do plan to enroll new subjects to keep the total number of subjects at up to 20 in case of attrition. If there is a sufficient number of new subjects enrolled to replace those that drop out, a new SMA group will be created so that newly enrolled subjects will be able to start the intervention from the baseline visit.

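### Dyads who leave early are never interviewed and have no planned exit rating, so Hypothesis 1b rests only on families still in the study at month 12

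*Combined protocol and SAP*

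**What the plan says.** Section 6.3 states: "Upon completion of the final SMA visit at month 12, dyads will be contacted to schedule a semi-structured interview". Section 4 repeats this, Table 1 marks the dyad interview in the 12-month column only, and Section 6.5 places it at the end of the study. Table 2 (Section 3.3) gives the interval for both the satisfaction ratings and the interview as "After completion of intervention".

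Hypothesis 1b (Section 8.2) reads: "Thematic analysis of semi-structured interviews will identify high satisfaction with SMA". The acceptability benchmark in Section 6.4 is ">80% reporting that they were satisfied and perceived utility and benefit as indicated by a Likert scale score of 4 or 5".

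The protocol foresees exits caused by the SMA itself. Section 2.3 gives families the "option to withdraw from the intervention at any time if they become uncomfortable with the lack of privacy in the SMA". Under Section 5.7, participants with significant distress from the intervention "will be terminated from study participation", and the reason for leaving goes on a case report form. Section 6.3 adds: "In the event of withdrawal or early termination, participants will be asked to come for an end of study visit". No section says what happens at that visit.

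Two other provisions matter. Table 1 and Sections 6.3 and 6.4 schedule an SMA Evaluation for youth and parent at every visit, emailed a week beforehand and completed in clinic if still outstanding. Section 8.3 sets a per-protocol analysis because usable data from withdrawals are said to be out of reach, then keeps partial data where it can. Sections 5.7 and 8.5 plan to replace leavers.

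**The concern.** Acceptability is half of the primary objective, and the interview is one of the measures named for it in Section 3.1. Families who leave because the group format exposes or upsets them hold the most direct evidence against acceptability, and the schedule has no point at which they are asked about it in depth. What they said on an interim form may predate the session that made them leave.

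The result could be a finding of high satisfaction that partly reflects who stayed, with privacy, distress and logistics under-represented in the themes. Section 2.4 says the pilot is meant to inform later randomized studies, so those are the barriers it most needs to record. An interview not held at exit cannot be recovered in the analysis.

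**Working it through.** There is no plan figure to reproduce. The sample size has no formula ("As this is a pilot study, we plan to enroll up to 20 parent-child dyads"), and the primary outcome has no null hypothesis, alpha or power. The check sets the provisions side by side and then does arithmetic on the protocol's own benchmark.

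**Interview.** It has one slot, after the month-12 SMA (Table 1; Sections 4, 6.3 and 6.5). No section offers it to a dyad that stops earlier.

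**Ratings from leavers.** A dyad leaving after the month-6 SMA could have up to three SMA Evaluations per respondent (initial, month 3, month 6). Because the form goes out before each visit, the first may be completed before any SMA has taken place and the last may predate the final session attended. None is assigned to the exit visit.

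**Ratings that count.** Table 2 points to ratings after the intervention. Section 8.3 is per protocol but admits partial data. No section names the SMA Evaluation or the denominator that decides the >80% benchmark.

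**Arithmetic.** Inputs: N = 20 dyads (Section 8.5); retention and acceptability both >80% (Sections 3.3 and 8.2). The number of leavers L is assumed, since Section 8.5 says only that dropout should be low. One rating per dyad is counted for simplicity.

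- Completers: c = 20 − L.
- Fewest satisfied completers that pass: s = floor(0.8c) + 1.
- All starters: s/20 if no leaver was satisfied, (s + L)/20 if all were.

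| L | Retention | s/c | All starters, no leaver satisfied | All starters, every leaver satisfied |
|---|---|---|---|---|
| 1 | 19/20 = 95% | 16/19 = 84.2% | 16/20 = 80% | 17/20 = 85% |
| 2 | 18/20 = 90% | 15/18 = 83.3% | 15/20 = 75% | 17/20 = 85% |
| 3 | 17/20 = 85% | 14/17 = 82.4% | 14/20 = 70% | 17/20 = 85% |

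With 4 leavers, retention is 16/20 = 80%, which no longer exceeds 80%. Three is therefore the most that can leave with the retention benchmark still met.

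**Replacement.** If 3 unsatisfied leavers are replaced and 17 of the 20 final dyads are satisfied, 17/20 = 85% passes, but among all who started it is 17/(20 + 3) = 17/23 = 73.9%.

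**Chance of passing.** Assume 3 leavers and that each of the 17 completers is satisfied with probability 0.85, independently. By exact binomial, the chance of at least 14 of 17 is 0.76. The chance of at least 17 of all 20 starters is 0.06, 0.22 or 0.39 if each leaver's probability is 0, 0.25 or 0.50. If leavers match completers at 0.85 it is 0.65; that remaining gap to 0.76 comes from the discrete threshold, with no bias in the estimated proportion.

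**The case against.** The strongest reply is that leavers are not silent. SMA Evaluations are scheduled at every visit, Section 8.3 keeps partial data, Section 5.6 has staff contact families about barriers after a missed session, withdrawal reasons are recorded, and retention is reported as its own benchmark. Withdrawing from the intervention, as Section 2.3 puts it, need not end survey follow-up. All of this stands. A reader might infer from Table 2 that satisfaction is rated only after month 12 and that leavers contribute nothing; Table 1 and Sections 6.3 and 6.4 contradict that.

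A reader might also infer that an upward bias is established, or that only families who sat through all five sessions are interviewed. Neither follows. The direction depends on leavers being less satisfied, for which the protocol has no figure. The interview is triggered by completing the month-12 SMA, so families who missed earlier sessions, or who stayed while dissatisfied, are included. Hypothesis 1b is also descriptive, with its null given as not applicable.

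These points do not fill the gap. Retention shows how many left but corrects neither the satisfaction proportion nor the themes. A reason on a form and a call about a missed session do not replace an interview. The interim forms are timed before visits, and no section says that they feed the benchmark.

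There is also a fair point about burden: some leavers will have been terminated for distress. That is why the contact should be an offer that they are free to decline.

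**Conclusion.** The concern holds for the interview. Followed as written, Hypothesis 1b draws only on dyads still in the study at month 12, although the protocol foresees exits caused by the SMA.

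For the ratings the defect is narrower: no exit rating, a conflict between Table 1 and Table 2 on when satisfaction is measured, a conflict between Section 8.3 and the exit visit in Section 6.3, and no stated time point or denominator for the >80% benchmark.

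With 3 of 20 leaving, a pass at 82% among completers is compatible with anything from 70% to 85% among starters. That range is an illustration resting on assumed leaver counts and satisfaction. An upward bias is plausible, most clearly for dyads terminated for distress, but it is conditional. The change is worth making because it is cheap and no later analysis can replace it.

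**What to change.** - **Section 6.3 and Table 1:** add an early-exit column. Offer the existing interview and the SMA Evaluation, voluntarily, at the end-of-study visit already planned, or by phone or REDCap for those who will not attend.
- **Table 2:** change the interval to after month 12 or at early exit.
- **Section 8.3:** reconcile the statement that withdrawal data cannot be obtained with the exit visit in Section 6.3.
- **Sections 3.3, 6.4 and 8.4:** calculate the >80% acceptability figure over all dyads that attended at least one SMA, including those later replaced, using the last available SMA Evaluation. State whether the 15- and 18-month forms count and how youth and parent ratings are handled. Add a sensitivity analysis that counts leavers without a rating as not satisfied.
- **Thematic analysis (Sections 8.2 and 8.4):** report themes from leavers and completers separately, and draw the Hypothesis 1b conclusion from both.

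The cost is an amendment needing IRB approval and a few extra contacts of about 45 minutes each, with the existing guide and staff. Some leavers will decline, so selection is reduced but not removed, and the satisfaction figure may be less favourable.
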